The overall purpose of this study is to examine the relationship between the “organic” and “natural” descriptors and health risk expectancies, subjective effects, topography, and resulting chemical exposures. This is a within-person human laboratory study with assessments of psychological, behavioral, and biological exposure data. The procedures described here were tested in a pilot study conducted in late 2019.³² Data will be collected at the University of Nevada, Reno (Reno, Nevada, USA), the Desert Research Institute (Reno, Nevada, USA), and the University of Pennsylvania (Philadelphia, Pennsylvania, USA). The study will consist of 5 total lab visits: the baseline visit, and four experimental visits (own brand comparator condition, “natural” advertising condition, “organic” advertising condition, and “conventional” advertising condition) (Figure 1). Conditions will be randomized and counterbalanced to account for order effects.

This is a deception study; participants will believe that they are participating in market testing cigarettes and will not know the real purpose of the study. We created a faux tobacco brand and associated cigarette mailer for the organic, natural, and conventional cigarette varieties (Figure 2). While participants will believe they are testing three varieties of a new brand of cigarette, in reality they will use the same product (Nat’s “Rich Smooth Taste” cigarettes, the blinded experimental cigarette) three times. None of the labs involved in data collection are in medical or public health-focused buildings, which aids in the study deception. Results from our pilot study demonstrate that this study design will deceive participants.³² At the last pilot study visit, we asked our 22 pilot study participants to restate the purpose of the study as they saw it. Though a handful of participants inferred that things weren’t *exactly* as they seemed, none of the participants described the actual study purpose. We will include the same question at the end of Session 5 to identify participants who were not deceived by the study (see Missing Data).

Aims & Hypotheses

Aim 1 hypotheses are primary; Aims 2 and 3 hypotheses are secondary. The specific aims and associated hypotheses are:

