Aim 1: Examine the association between exposure to “natural” or “organic” cigarette descriptors and: 1) health risk expectancies (e.g., chemical content); 2) subjective effects of smoking (e.g., chemical taste); 3) smoking topography (e.g., total puff volume); and 4) biomarkers of exposure (e.g., salivary aldehydes).

H_{1.1}: More participants will rate cigarettes in the “natural” and “organic” conditions as having fewer chemicals relative to cigarettes in the “conventional” condition.

H_{1.2}: Participants’ average ratings of the “chemical aftertaste” of the cigarettes in the “natural” and “organic” conditions will be higher (e.g., closer towards the “less chemical aftertaste” side of the scale) relative to their average ratings of the cigarette in the “conventional” condition.

H_{1.3}: Total puff volume will be higher in the “natural” and “organic” conditions than the “conventional” condition.

H_{1.4}: Change in salivary aldehyde concentrations pre/post administration of the study cigarette(s) will be higher in the “natural” and “organic” conditions than the “conventional” condition.

Aim 2: Examine whether the relationships in Aim 1 differ by preference for a “natural/organic” cigarette brand (NAS smokers vs. non-NAS smokers).

H_{2.1}: Compared to non-NAS smokers, more NAS smokers will rate the “natural” and “organic” conditions as having fewer chemicals relative to their ratings in the “conventional” condition, but not relative to their own brand condition.

H_{2.2}: Compared to non-NAS smokers, NAS smokers’ average ratings of the “chemical aftertaste” of the cigarettes in the “natural” and “organic” conditions will be higher (e.g., closer towards the “less chemical aftertaste” side of the scale) relative to their average ratings of the cigarette in the “conventional” condition, but not relative to their own brand condition

H_{2.3}: NAS smokers’ total puff volume will be lower in the “conventional” condition than the “natural,” “organic,” and own brand conditions.

H_{2.4}: NAS smokers’ change in salivary aldehyde concentrations pre/post study cigarette(s) administration will be lower in the “conventional” condition than the “natural,” “organic,” and own brand conditions.

Aim 3: Examine if relationships in Aim 1 differ by gender.

H_{3.1}: A greater proportion of women than men will rate the cigarettes in the “natural” and “organic” conditions as having fewer chemicals relative to cigarettes in the “conventional” condition.

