We will consider models that: 1) allow the effect of the condition (conventional, organic, and natural) to differ based on NAS-smoking status and gender (as hypothesized); 2) allow the effect of the condition to differ based only on NAS-smoking status; 3) allow the effect of the condition to differ based only on gender; and 4) do not allow the effect of the condition to differ based on NAS-smoking status or gender. We will also consider models that combine the effects of the natural and organic conditions, as we believe the effects of these two conditions could be similar for our outcomes. We will also consider in the model an effect for the own brand

condition (which may or not depend on NAS-smoking status and gender), period effects, random effects, and effects for other covariates that may be predictive of the outcome. Bayes factors will be used to determine if the effect of the condition depends on NAS-smoking status or gender, and if a combined effect (one effect vs two) should be used in the model for the natural and organic conditions.

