95% credible intervals will be estimated for the difference in effects between 1) 4. - 2. and 8. - 6., 2) 3. - 2. and 7. - 6, 3) 4. - 1. and 8. - 5., and 4) 3. - 1. and 7. - 5. If the credible interval in 1) does not contain 0, then there is evidence (against the null hypothesis) that NAS and non-NAS smokers differ in their mean organic condition outcomes relative to their conventional condition outcomes (otherwise there is evidence for the null hypothesis and therefore no

difference in these two groups). If 2) does not contain 0, then there is evidence (against the null hypothesis) that NAS and non-NAS smokers differ in their mean natural condition outcomes relative to the conventional condition outcomes (otherwise there is evidence for the hull hypothesis and therefore no difference in these two groups). If 3) does not contain 0, then there is evidence (against the null hypothesis) that NAS smokers and non-NAS smokers differ in their mean organic condition outcomes relative to their own brand condition outcomes (otherwise there is evidence for the hull hypothesis and therefore no difference in these two groups). If 4) does not contain 0, then there is evidence (against the null hypothesis) that NAS smokers and non-NAS smokers differ in their mean natural condition outcomes relative to their own brand condition outcomes (otherwise there is evidence for the hull hypothesis and therefore no difference in these two groups). H(2.1) and H(2.2) hypothesizes that there will be evidence against the null hypothesis in 1) and 2) but evidence for the null hypothesis in 3) and 4).

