To test H(2.3) and H(2.4), we will estimate the 95% credible intervals corresponding to the difference in means between 6) 4. and 2. above, 7) 3. and 2, 8) 4. and 1., and 9) 3. and 1. If the credible interval in 6) / 7) / 8) / 9) does not contain 0, then there is evidence that NAS smokers mean outcome under the organic / natural / organic / natural condition is significantly different than NAS smokers mean outcome under the conventional / conventional / own brand / own brand condition (evidence against null), otherwise there is evidence that NAS smokers mean outcome is no different in the organic / natural / organic / natural condition compared to the convention / conventional / own brand / own brand condition (evidence for null). We hypothesize that the organic and natural conditions will differ from the conventional condition (i.e. evidence against null in 6) and 7)) but not the own brand condition (i.e. evidence for null in 7) and 8)).

To test H(3.1)-H(3.4), we will estimate effects for the following subgroups:

1. effect of men smokers under the own brand condition
2. effect of men smokers under the conventional condition
3. effect of men smokers under the natural condition
4. effect of men smokers under the organic condition
5. effect of women smokers under the own brand condition
6. effect of women smokers under the conventional condition
7. effect of women smokers under the natural condition
8. effect of women smokers under the organic condition

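### For Aim 2, any 95% credible interval that contains 0 is read as support for no difference, and the conventional versus own-brand part of H2.3/H2.4 is never tested

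*Combined protocol and SAP*

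**What the plan says.** All references are to the combined protocol and SAP.

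- **Status of the aim.** "Aim 1 hypotheses are primary; Aims 2 and 3 hypotheses are secondary" (Aims & Hypotheses).
- **H2.1/H2.2, as hypothesised.** NAS smokers should differ from non-NAS smokers in their natural and organic ratings relative to conventional, "but not relative to their own brand condition".
- **H2.1/H2.2, as tested** (Hypothesis testing). Contrasts 1) and 2) compare the groups on organic and natural relative to conventional. Contrasts 3) and 4) do so relative to own brand. An interval excluding 0 counts against the null; "otherwise there is evidence for the hull hypothesis and therefore no difference in these two groups". The hypotheses are said to require "evidence for the null hypothesis in 3) and 4", which are the own-brand contrasts.
- **H2.3, as hypothesised.** "NAS smokers’ total puff volume will be lower in the “conventional” condition than the “natural,” “organic,” and own brand conditions". H2.4 predicts the same ordering for the change in salivary aldehydes.
- **H2.3/H2.4, as tested.** Within NAS smokers, contrasts 6) and 7) set organic and natural against conventional; 8) and 9) set them against own brand. If the interval contains 0, "otherwise there is evidence that NAS smokers mean outcome is no different in the organic / natural / organic / natural condition" relative to the comparator. Organic and natural are expected to differ from conventional "but not the own brand condition (i.e. evidence for null in 7) and 8".
- **Bayes factors** (Statistical analyses). "Bayes factors will be used to determine if the effect of the condition depends on NAS-smoking status or gender". They also decide whether natural and organic share one effect. They are not attached to any of contrasts 1) to 9).

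**The concern.** The rule has two outcomes, against the null or for it, and no inconclusive one. An interval contains 0 either because the true difference is small or because the data are imprecise, and the rule treats both as support for no difference. The own-brand part of H2.1/H2.2 depends on this reading, so imprecision helps to confirm a hypothesis.

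For H2.3/H2.4 the analysis does not match the hypothesis. The hypothesis puts conventional below own brand; no interval compares those two conditions. The analysis adds a prediction that natural and organic do not differ from own brand, and judges it by the same faulty rule.

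At stake is a published statement that NAS and non-NAS smokers do not differ, or that the labelled cigarette does not differ from NAS smokers' own brand, resting only on a wide interval.

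**Working it through.** **Inputs** (Sample size calculations): at least 228 completers in two equal groups, taken here as 114 per group; intraclass correlation 0.5; puff-volume difference 120 ml with SD 165 ml; stress case with the effect halved (60 ml) and the covariance 50% larger, so SD = 165 × √1.5 = 202 ml. Assumed: two-sided 5%, normal approximation, no shrinkage from model averaging or multiplicity. Under uninformative priors the plan itself equates a single-model analysis with maximum likelihood, so the intervals should behave much like 95% confidence intervals.

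**The plan's own figure.** SD of a within-person difference = 202.1 × √(2 × (1 − 0.5)) = 202.1 ml. n = [202.1 × (1.960 + 1.282) / 60]² = 119.2, so 120, as stated for Aim 1. The inputs are being read as intended.

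**Between groups, contrasts 3) and 4)**, in SDs of the within-person difference. SE = √(2/114) = 0.1325; half-width = 1.96 × 0.1325 = 0.260. The chance that the interval contains 0 is approximately Φ(1.96 − gap/SE):

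| True gap (SD) | Declared no difference |
|---|---|
| 0.20 | 67% |
| 0.26 | 50% |
| 0.297 (60/202) | 39% |
| 0.364 (60/165) | 22% |
| 0.43 | 10% |

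The rule rewards small samples. With a true gap of 0.2 SD on both own-brand contrasts (correlation 0.5 between them), both intervals contain 0 in 53% of trials with 228 subjects, 73% with 100 and 84% with 40.

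**Full H2.2 pattern** (1 and 2 exclude 0, 3 and 4 contain 0), by simulation with equal correlation 0.5. If the true own-brand gap is 0.364 or 0.297 SD and the gap relative to conventional is twice that, the pattern is wrongly confirmed in about 10% or 23% of trials. If the two gaps are equal, the figures are 5% and 8%. The gap sizes and the ratio are assumptions; no aftertaste SD is given.

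**Within NAS smokers, contrasts 8) and 9), puff volume, true gap 60 ml.** SD of difference = SD × √(2 × (1 − ρ)), SE = SD of difference / √114:

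| ρ | SD of difference (ml) | SE (ml) | Declared no different |
|---|---|---|---|
| 0.3 (assumed) | 195 to 239 | 18.3 to 22.4 | 9% to 24% |
| 0.5 (plan) | 165 to 202 | 15.5 to 18.9 | 3% to 11% |
| 0.7 (assumed) | 128 to 157 | 12.0 to 14.7 | 0.1% to 1.6% |

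For a smaller true gap of 30 ml at ρ = 0.5, the figure is 51% to 65%.

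**Hypothesis against test, H2.3/H2.4.** The hypothesis needs three comparisons within NAS smokers: conventional against natural, organic and own brand. Contrasts 6) and 7) supply the first two. Nothing supplies the third (effect 2 against effect 1). It cannot be inferred from the others: organic differing from conventional, together with organic versus own brand containing 0, does not establish that conventional differs from own brand.

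**Labels.** Contrast 7) is listed both as expected against the null and as expected for it; by the section's own list the own-brand pair is 8) and 9). Label 5) is unused, and 9) is used again for a gender contrast under Aim 3.

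**The case against.** Several limits are fair.

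- **Bayes factors are in the plan.** If model selection drops NAS dependence for both the condition and own-brand effects, contrasts 1) to 4) are zero by construction, and that null rests on a Bayes factor. This stands only in part: such a model cannot yield the hypothesised pattern, with 1) and 2) non-null and 3) and 4) null.
- **The consequences are contained.** Aim 2 is secondary, and the plan reports 95% credible intervals and can show posterior figures, so a reader could see the imprecision. True, but the written rule still prescribes the wrong conclusion.
- **The illustrations depend on assumed sizes.** The 0.30 to 0.36 SD gaps come from puff volume and are only indicative for aftertaste. For puff volume within NAS smokers, a 60 ml gap is seldom missed at the plan's correlation. The practical risk lies mainly in the between-group contrasts.
- **H2.1 may need separate handling.** The expectancy item already compares the study cigarette with the participant's own. The Measures text does not say how it is scored for own brand, and I could not see Table 2. Whether contrasts 3) and 4) can be estimated for H2.1 is unclear.
- **The added own-brand null does not contradict the hypothesis.** It goes beyond the stated ordering. The omitted comparison is still a real gap.
- **The label slips are editorial** and carry no weight in the conclusion.

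**Conclusion.** The concern holds and should be fixed. The rule as written turns failure to exclude 0 into a finding of no difference, and the own-brand part of H2.1/H2.2 takes that as its success criterion. With 114 per group, a true between-group gap equal to the half-width, 0.26 SD, is declared absent half the time, and a gap must reach about 0.43 SD before that falls to 10%. Within NAS smokers the risk for a 60 ml puff-volume gap is 3% to 11% at correlation 0.5, and it depends strongly on that correlation. These figures rest on the assumptions listed above. None is offered in the units of the binary, aftertaste or aldehyde outcomes, whose SDs or rates are not given. Separately, one stated part of H2.3/H2.4 has no test. Confidence is high, because the main points can be read directly from the text. Aim 1 is not affected.

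**What to change.** 1. **Change the rule for Aim 2.** Where an interval contains 0, say that the result is inconclusive. Claim no difference only if a criterion stated before analysis is met, for example the whole 95% credible interval lying inside a justified margin on the scale analysed. Without such a criterion, report the interval and make no such claim.
2. **Align H2.3/H2.4 with their test.** Add conventional versus own brand within NAS smokers (effect 2 against effect 1), for which label 5) is free. If the own-brand null is kept, state it as an additional prediction.
3. **Correct the labels.** The own-brand pair is 8) and 9); renumber the Aim 3 contrasts so that 9) is not used twice.

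**Cost.** The inconclusive wording, the extra contrast and the renumbering are text edits using the same posterior draws. The extra contrast would exclude 0 for a true 60 ml difference in 89% to 97% of trials at correlation 0.5, or 76% to 91% at 0.3.

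A criterion for no difference costs more. The plan allows log-transformed or dichotomised outcomes and measures two aldehydes, so each scale that may be used needs its own margin. Some own-brand claims will become inconclusive. For an 80% chance per contrast of claiming no difference when the truth is 0, the margin must be about (1.96 + 1.2816) × 0.1325 = 0.43 SD between groups, or (1.96 + 1.2816)/√114 = 0.30 SD (50 to 61 ml) within NAS smokers. Using a 90% interval instead (1.645 in place of 1.96) gives about 0.39 SD and 45 to 55 ml. The documents do not establish that differences of these sizes are negligible, so the sponsor would have to justify them.

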95% credible intervals will be estimated for the difference in effects between 9) 4. - 2. and 8. - 6., 10) 3. - 2. and 7. - 6., 11) 4. - 1. - (2. - 1.) and 8. - 5. - (6. - 5.), and 12) 3. - 1. - (2. - 1.) and 7. - 5. - (6. - 5.). If the credible interval in 9) / 10) does not contain 0, then there is evidence that men smokers mean outcome under the organic / natural condition relative to the convention condition differs from the women smokers mean outcome under the organic / natural condition relative to the convention condition, which would provide evidence against the null hypothesis in H(3.1) and H(3.2). If the credible interval in 11) / 12) does not contain 0, then there is evidence that men smokers mean outcome difference between the organic / natural condition relative to the own brand condition and convention condition relative to own brand condition differs from the women smokers mean outcome difference between the organic / natural condition relative to the own brand condition and convention condition relative to own brand condition, which would provide evidence against the null hypothesis in H(3.3) and H(3.4) (assuming the direction of the difference is not opposite the hypothesized direction).

Biomarker analyses

Previous work, including our preliminary biosample analyses, demonstrate that short exposures similar to our 15 min ad lib bout increase exposure biomarkers like saliva nicotine (>200-fold) and aldehydes (2-10-fold).^{54,55} Participants' saliva samples (before and after tobacco use sessions) will be characterized for nicotine and aldehyde concentrations and compared across descriptor conditions.

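### The analysis listed for H2.3 and H2.4 omits the own-brand versus conventional comparison that the hypotheses state, adds an own-brand null that they do not state, and reads an interval containing 0 as no difference

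*Combined protocol and SAP*

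**What the plan says.** In Aims & Hypotheses, H2.3 reads "NAS smokers’ total puff volume will be lower in the “conventional” condition than the “natural,” “organic,” and own brand conditions". H2.4 has the same form for aldehydes: "change in salivary aldehyde concentrations pre/post study cigarette(s) administration will be lower in the “conventional” condition than the “natural,” “organic,” and own brand" conditions. Each therefore holds three directional comparisons within NAS smokers. Neither says that the labelled cigarettes will match own brand. That idea belongs to H2.1 and H2.2, which end "but not relative to their own brand condition".

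In Hypothesis testing, the NAS effects are numbered 1. own brand, 2. conventional, 3. natural and 4. organic. H2.3 and H2.4 are to be tested from the "difference in means between 6) 4. and 2. above, 7) 3. and 2, 8) 4. and 1., and 9) 3. and 1". The predicted result is "evidence against null in 6) and 7)) but not the own brand condition (i.e. evidence for null in 7) and 8"). When an interval includes 0, the text concludes that "otherwise there is evidence that NAS smokers mean outcome is no different in the organic / natural / organic / natural condition" compared with its comparator. The paragraph on H2.1 and H2.2 uses the same logic: it "hypothesizes that there will be evidence against the null hypothesis in 1) and 2) but evidence for the null hypothesis in 3) and 4").

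For H3.3 and H3.4 the section adds a proviso on sign, "assuming the direction of the difference is not opposite the hypothesized direction". The H2.3/H2.4 paragraph has none, although those hypotheses also state a direction.

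**The concern.** Someone who follows the Hypothesis testing section to the letter would report four contrasts for H2.3, and four for H2.4, without examining one of the three comparisons in the hypothesis. Two of the four would address an expectation that the hypothesis does not contain. The two sections therefore do not describe the same hypothesis, and a report could follow either.

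The reading of null results is a separate problem. Without a margin, a wide interval counts towards no difference just as a narrow one around 0 does. For contrasts 3), 4), 8) and 9) that is the predicted outcome, so imprecision would be credited as confirmation. For 1), 2), 6) and 7) it would turn a failure to detect into a claim of absence.

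**Working it through.** **1. Stated and planned comparisons, NAS smokers**

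| Comparison | In H2.3/H2.4 | In Hypothesis testing |
|---|---|---|
| organic − conventional (4. − 2.) | yes | contrast 6) |
| natural − conventional (3. − 2.) | yes | contrast 7) |
| own brand − conventional (1. − 2.) | yes | none |
| organic − own brand (4. − 1.) | no | contrast 8), predicted null |
| natural − own brand (3. − 1.) | no | contrast 9), predicted null |

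No other part of the section supplies 1. − 2. The Aim 1 intervals are limited to organic and natural minus conventional. The H2.1/H2.2 contrasts compare NAS with non-NAS smokers. The gender contrasts 11) and 12) contain 2. − 1., but own brand cancels within each. The difference follows by subtraction, (4. − 2.) − (4. − 1.) = 1. − 2., but its interval cannot be read from the listed intervals.

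**2. Numbering.** Contrast 7) is assigned to both sides of the prediction and 9) to neither. The wording about own brand shows that 8) and 9) were meant.

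**3. Is 1. − 2. estimable?** Study procedures fixes own brand at Session 2 and the three labelled conditions at Sessions 3-5. Statistical analyses says period effects will be considered, without giving their form. I took all six orders of Sessions 3-5, with four condition and four session indicators. The design has rank 6. Organic − conventional lies in its row space; own brand − conventional and organic − own brand do not. Own brand and Session 2 are the same column, so with a free Session 2 effect only their sum can be compared with the labelled conditions. Contrasts 8) and 9) have the same limit.

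**4. Inputs for the illustration.** Sample size calculations gives a mean difference of 120 ml, SD 165 ml, a version with the effect halved (60 ml) and covariance 50% larger, and 120 subjects for 90% power. Reproducing that: 165 × √1.5 = 202.1 ml, and (202.1 × (1.960 + 1.282) / 60)² = 119.2, so 120. The figure agrees with 165 ml used as the SD of a within-person difference (or as a raw SD with intraclass correlation 0.5). I assume 228 / 2 = 114 NAS smokers and the same variance for own brand. Brackets use 202.1 ml.

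**5. Reading an interval that contains 0**
- SE = 165 / √114 = 15.45 ml (18.93).
- Half-width = 1.96 × SE = 30.3 ml (37.1).
- P(contains 0 given true 30 ml) = Φ((30.3 − 30) / 15.45) − Φ((−30.3 − 30) / 15.45) = 0.507. With the larger covariance it is 0.646.
- If 165 ml is a raw SD: 0.625 (0.732) at intraclass correlation 0.3, and 0.292 (0.466) at 0.7.

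**6. When does the missing contrast matter?** I simulated four condition means under compound symmetry, with conventional at 0 and natural = organic = +60 ml. The pattern is: 6) and 7) exclude 0, 8) and 9) contain it.
- Own brand +60 ml, the state that the plan predicts: pattern met in 87% (75%) of trials; 1. − 2. contains 0 in 1.3% (about 5%) of those.
- Own brand +30 ml: pattern met in 32% (38%); 1. − 2. contains 0 in 22% (about 36%) of those, which is 7% (14%) of all trials.

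The simulation omits the Bayes-factor model choice, model averaging and multiplicity adjustment. The plan gives no aldehyde SD, so nothing is computed for H2.4.

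**The case against.** The strongest reply is that little is lost. Effects 1. and 2. are both in the model, 95% credible intervals are already planned, and own brand has a mainly descriptive role in Study procedures. If the plan's prediction is true, a trial that shows the pattern will nearly always show own brand above conventional as well (step 6). This stands, and it limits the size of the point. It does not supply an interval or rule for a comparison that the hypotheses state.

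It is also true that the comparison is not a clean one. Own brand is a different product smoked at a fixed visit, so a visit-order effect alone could put 1. − 2. above 0. That argues for a caveat, or for removing own brand from the hypotheses, rather than for leaving the sections in conflict.

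The numbering slip is minor, since the intent can be recovered. The missing sign rule is minor too: a signed interval shows direction, and other contrasts in the section also lack the proviso.

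Two stronger readings should be resisted. First, a reader might infer that the two sections would return opposite verdicts on the same data. With own brand at +120 ml and the labels at +60 ml, all three stated comparisons are shown in 95% (81%) of trials, while the predicted pattern occurs in 0.5% (about 4%). But the plan reads each interval separately, and the pattern is a prediction. Nothing says that H2.3 fails if 8) or 9) excludes 0, and 6) and 7) would still support it. Second, a reader might infer that moderation by NAS status goes untested for these outcomes because the contrasts are within NAS smokers. NAS-only contrasts fit the wording of H2.3 and H2.4, and Bayes factors assess moderation for every outcome.

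**Conclusion.** The point holds on the text. One of three stated comparisons has no interval or rule for each of two secondary outcomes. Two of the four listed contrasts address an expectation not stated for those outcomes. The prediction is misnumbered. The rule equating an interval containing 0 with no difference applies to all of contrasts 1)-4) and 6)-9).

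The practical effect is modest. The omitted contrast matters mainly if own brand differs from the labelled cigarettes. Even if added, it describes label, product and visit together unless the period model is restricted. The null-reading rule is the more consequential part: about 51% (65%) for a true 30 ml difference, with a range of 29% to 73% over the settings tried. These figures rest on 114 NAS smokers, the plan's 165 ml, a normal approximation and an illustrative 30 ml. I rate it minor to should-fix. The primary Aim 1 analysis is not affected.

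**What to change.** 1. Reconcile Aims & Hypotheses with Hypothesis testing. Either add 1. − 2. in NAS smokers for puff volume and aldehyde change, with direction in the rule (interval entirely above 0, also for 6) and 7)), or remove own brand from H2.3 and H2.4. If it is added, say whether all three comparisons are required and how period enters the model, and report 1. − 2., 8) and 9) as descriptive of label, product and visit combined.
2. Drop the own-brand null for H2.3 and H2.4, or keep 8) and 9) as separately labelled contrasts with the prediction renumbered to them. The label 9) is used again for the first gender contrast, so make the labels unique.
3. For 1)-4) and 6)-9), call an interval containing 0 inconclusive. Claim no difference only when the interval lies inside a margin fixed in advance.

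The cost is SAP wording and at most one more interval per outcome, from data and models already planned. If 1. − 2. is added, the list has five contrasts with 8) and 9) kept or three with them dropped, against four now, within the existing Aim 2 multiplicity approach. Design and sample size do not change.
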